6.2.1.3 Secondary analysis of primary efficacy variables

As a secondary analysis pairwise comparisons of the active neladenoson bialanate dose groups with the placebo group will be performed without controlling the family-wise error rate, by calculating the 90% confidence interval for the difference in primary efficacy variable between each active dose of neladenoson bialanate and placebo.

6.2.1.4 Sensitivity analyses of primary efficacy variables**6.2.1.4.1 Sensitivity analysis of primary efficacy variables in PPS LVEF and PPS BNP**

As a sensitivity analysis, primary analysis of primary efficacy variables on the “completers and treatment adherers” excluding the censored patients in the per-protocol analysis set will be repeated. This strategy leads to unbiased estimates only if missing values are “missing completely at random” (MCAR), i.e. the missingness – including missing data due to death – is independent of both observed and unobserved outcomes. This condition is unlikely to hold exactly but rather approximately.

Further sensitivity analyses on the PPS LVEF and PPS BNP may be performed if the missing data patterns suggest further exploration.

6.2.1.4.2 Sensitivity analysis of primary efficacy variables in FAS

Additional efficacy analyses in the FAS will include the following:

- Primary analyses of primary efficacy variables specified in section 6.2.1.2 will be performed in FAS without any imputation.
- Generally, it will be assumed that missing observations for the respective efficacy variables are missing at random. This implies that the behavior of the post dropout observations can be predicted from the observed variables using appropriate imputation models. Likely exceptions to the missing at random assumption are observations which are missing due to a patient’s CV death or HF hospitalization prior to the visit in Week 20. These observations can be assumed to be missing not at random (MNAR), i.e., that missingness depends both on observed and unobserved outcomes and that an explicit model for the patient’s statistical behavior after drop-out (or death) is required. Therefore, an analysis based on a pattern mixture framework (6) with different imputation rules depending on the reason for missingness will be used using a multiple imputation model, followed by a modification of the imputed data applying penalties:
 1. First, multiple imputation will be applied to draw sets of completed data, using an appropriate imputation model. Baseline characteristics which should be considered in the imputation model include but are not restricted to the baseline values of the respective efficacy variable, the treatment group, and sex.
 2. The imputed data will be modified by applying penalties. The penalty is chosen as the median of the worst changes from baseline across treatment groups (or 0 if the median worst change should be positive for LVEF or negative for LVESV/LVEDV or log-transformed NT-proBNP/hs-TNT).

3. After modifying the completed data sets, the primary analysis specified in section 6.2.1.2 will be applied to the multiple imputed datasets and the point estimate and variance of the contrast from multiple imputed datasets will be combined based on Rubin's rule (8). For more details see Appendix 9.4.
- Primary analyses where for each patient without an observation at the visit in Week 20 the missing value will be imputed according to a last observation carried forward approach, including the baseline value.

For reproducibility, the SAS seed number for creating the random numbers for the multiple imputation will be set to the study number.

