6.4 Withdrawal of patients from study

6.4.1 Withdrawal

This section was changed in Amendment 2, see Section 15.1 for details.

An excessive rate of withdrawals (either patients discontinuing study medication or study withdrawal) can render the study non-interpretable. Therefore, un-necessary withdrawal of patients should be avoided and all efforts should be taken to motivate patients to comply with all the study specific procedures and to be followed until the end of the trial to detect the occurrence of cardiovascular events / assess vital status.

Before permanently discontinuing study medication (either initiated by the patient or the investigator) an interruption should be considered. Patients, who have temporarily discontinued study medication for any reason, should restart as soon as medically justified in the opinion of the investigator; the patient can re-start at any time before the end of treatment

(EOT) visit. In addition, patients should not be withdrawn from the study drug or from the study solely due to reaching a potential cardiovascular event.

All patients who permanently discontinue study medication should come in for the EOT / premature discontinuation visit as soon as possible after discontinuation of the study medication and the safety follow-up visit 4 weeks after the last dose. In addition, they will be contacted by the investigator via the scheduled Week 26 phone call to assess occurrence of cardiovascular events.

The investigator should show due diligence and explore all possible options to reach a patient who fails to return to a visit. The site must document all attempts to try to contact the patient in the medical records / source documents.

In order to avoid loss-to-follow-up, the investigator should ask the patient at the study start for the contact details of a relative or friend who can be contacted in case the patient cannot be reached.

Patients should not be withdrawn from follow-up unless the patient explicitly withdraws consent to be contacted. All efforts should therefore be made to minimize the number of patients who withdraw such consent as, in general, no further information on cardiovascular events and survival status may be collected after that point.

Withdrawal criteria

Patients **must be withdrawn from the study** if any of the following occurs:

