10.3.2 Statistical and analytical plans

All data will be listed and all variables will be summarized by means of descriptive statistics according to their type.

Summaries by treatment group using appropriate descriptive statistics will be provided for all study variables including demographic and baseline characteristics. Summary statistics will be presented for the original data as well as for the difference to baseline. Descriptive statistics such as arithmetic mean (or geometric mean, if applicable), median, standard deviation, quantiles, minimum, and maximum will be used to summarize continuous variables. Counts and percentages will be used to summarize categorical variables. Life tables and Kaplan-Meier estimates will be used to summarize time-to-event variables. Graphical data displays may also be used to summarize the data. Confidence intervals will be provided at a 2-sided level of 90% unless otherwise stated.

For this combined proof-of-concept and dose-finding study, an overall one-sided type I error level of 5% is planned to be used. The type I error will be controlled for the primary analysis of the primary variables.

There will be no formal control of the type I error for secondary or explorative analyses of the primary variables and any analysis of other efficacy variables.

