- the expected mean effect under the placebo dose is conservatively assumed as an absolute increase from baseline of up to $\Delta = 2\%$ with a standard deviation of $\sigma = 7\%$
- while the maximum observable mean effect under neladenoson bialanate within the dose range considered is assumed as an absolute increase of $\Delta = 5\%$ with a standard deviation of $\sigma = 7\%$.

This results in an expected maximum effect size of $(5-2)/7 = 3/7 = 0.43$ under conservative assumptions. Note that the threshold of clinical relevance is an absolute difference of 3% in the change from baseline over the placebo control group.

NT-proBNP: The following assumptions were made for the absolute change from baseline in the log-transformed NT-proBNP over 20 weeks:

- the expected mean effect under the placebo dose is assumed as an absolute decrease from baseline of $-0.105 \log(\text{pg/mL})$ with a standard deviation of $\sigma = 0.85 \log(\text{pg/mL})$, which is equivalent to a 10% relative reduction from a mean of 2,500 pg/mL at baseline.
- while the maximum observable mean effect under neladenoson bialanate within the dose range considered is assumed as an absolute decrease from baseline of $-0.357 \log(\text{pg/mL})$ with a standard deviation of $\sigma = 0.85 \log(\text{pg/mL})$, which is equivalent to a 30% relative reduction from a mean of 2,500 pg/mL at baseline.

It is assumed that the respective primary response efficacy variable, denoted as Y , is observed for the 6 parallel groups corresponding to doses levels: (placebo =) $d_1 < d_2 < \dots < d_k$, where $k = 6$.

For patient j within treatment group i the response can then be described by the following model:

$$Y_{ij} = f(d, \boldsymbol{\theta}) + \varepsilon_{ij}, \quad \varepsilon_{ij} \sim N(0, \sigma^2), \quad i = 1, \dots, k, \quad j = 1, \dots, n_i,$$

[figure not shown]
where $f(\cdot)$ is parameterized by a vector of parameters $\boldsymbol{\theta}$ and ε_{ij} is the error term.

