A candidate set with $M=5$ different dose response shapes $f(\cdot)$ based on four models was chosen for the MCP-Mod method. Table 10–1 displays the response expressions for the shapes in the candidate sets for both, change in LVEF and change in log-transformed NT-proBNP. Figure 10–1 shows the corresponding dose-response shapes for change in LVEF. The model parameters were obtained through discussions with experts in the clinical team, taking prior beliefs and uncertainty into account. The dose-response shapes for NT-proBNP are equivalent to those for LVEF but with decreasing trends.

Table 10–1: Dose-response shapes used in the candidate set

Model	Response as function of dose d	
	LVEF	NT-proBNP
Linear	$2 + 0.075d$	$-0.105 - 0.0063d$
Sigmoidal E_{\max} 1	$2 + 3.007689d^4 / (9^4 + d^4)$	$-0.105 - 0.2526d^4 / (9^4 + d^4)$
Sigmoidal E_{\max} 2	$2 + 3.375d^3 / (20^3 + d^3)$	$-0.105 - 0.2835d^3 / (20^3 + d^3)$
E_{\max}	$2 + 3.09375d / (1.25 + d)$	$-0.105 - 0.2599d / (1.25 + d)$
Quadratic	$2 + 0.2d - 0.00333d^2$	$-0.105 - 0.0168d + 0.00028d^2$

Figure 10–1: Dose-response shapes used in the candidate set for change in LVEF

Abbreviations: LVEF = left ventricular ejection fraction

Based on the standardized versions of the models in the candidate set and the sample size allocation planned for this study, the optimum contrast coefficients for the 5 contrast tests on the dose-response shapes can be derived for both primary variables.

Analysis

Step 1: Detection of dose-response signal

For detecting an overall trend, or a dose-response signal, each of the $M=5$ dose-response shapes in the candidate set will be tested, using a single contrast test based on the updated version of contrast coefficients taking the actual sample sizes per treatment group into account.

For each model m , $m = 1, \dots, 5$, in the candidate set

the null hypothesis $H_{0m}: c_m \mu_m^0 = 0$

will be tested against

the respective 1-sided alternative hypothesis $H_{1m}: c_m \mu_m^0 > 0$,

where $\mu_m^0 = (\mu_{m1}^0, \dots, \mu_{m6}^0)' = (f_m^0(d_1, \theta_m^0), \dots, f_m^0(d_6, \theta_m^0))'$ and

f^0 is the standardized version of the dose-response model $f(d, \theta) = \theta_0 + \theta_1 f^0(d, \theta^0)$. In this parameterization, θ_0 is a location parameter and θ_1 is a scale parameter such that only θ^0 determines the shape of the model function.

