The primary efficacy analysis aims at evaluating the dose-response relationship of the primary and secondary efficacy variables (except for clinical outcomes) for all randomized patients who have remained in the study and adhered to study treatment according to the study protocol until Week 20 (“completers and treatment adherers” analysis). Therefore, the primary analysis will be performed in the per-protocol set, a subset of the FAS comprising “compliant and adherent” patients (as much as possible, defined via validity criteria). To avoid bias, the PPS will also include those “compliant and adherent” patients who are “censored” due to CV death or a hospitalization for HF preventing the assessment of the relevant efficacy endpoints 20 weeks after randomization to take place as planned. It is expected that these are the only patients for whom missing observations need to be considered in the primary analysis. A “worst case” approach will be used, where the missing change from baseline value will be imputed with a multiple of the worst change from baseline value, which is possible given the individual baseline value observed in the respective treatment group, or 0 if the worst change in that treatment group is positive for LVEF / negative for NT-proBNP.

As a sensitivity analysis, a “completers and treatment adherers” only analysis excluding the censored patients in the per-protocol analysis set will be performed. This strategy leads to unbiased estimates only if missing values are “missing completely at random” (MCAR), i.e. the missingness – including missing data due to death – is independent of both observed and unobserved outcomes. This condition is unlikely to hold exactly but rather approximately.

Further sensitivity analyses on the PPS may be performed if the missing data patterns suggest further exploration.

Efficacy analysis using the FAS

The efficacy analysis in the FAS aims at evaluating the dose-response relationship of the primary and secondary efficacy variables for all randomized patients. Efficacy analyses in the FAS will include the following:

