10.4 Determination of sample size

In the first step, this combined proof-of-concept and Phase IIb dose-finding study has been powered for the detection of a dose response signal in the primary efficacy variable change in LVEF.

The sample size for the primary efficacy variable change in LVEF was evaluated under the assumptions described in Section 10.3.2.2 and a type I error level = 5% with the aim to achieve at least 80% power for the one-sided primary multiple contrast test. The overall randomization ratio was assumed to be 3:1:2:2:2:2 for doses 0, 5, 10, 20, 30, and 40 mg.

Table 10–2 displays the power for the multiple contrast test in the MCP-Mod approach, used as primary analysis, for the set of specified alternatives.

Table 10–2: Power for multiple contrast test for set of different alternatives

Sample size		Power for alternative based on respective dose-response model (in %)					
Overall	Per group ^a	Linear	Sigmoidal E _{max} 1	Sigmoidal E _{max} 2	E _{max}	Quadratic	Minimum
240	40	73.36	86.24	81.20	82.26	79.97	73.36
252	42	75.26	87.73	82.94	83.94	81.70	75.26
264	44	77.10	89.13	84.58	85.58	83.31	77.10
276	46	78.71	90.30	85.97	86.94	84.70	78.71
288	48	80.31	91.39	87.30	88.25	86.09	80.31
300	50	81.62	92.27	88.42	89.32	87.24	81.62
312	52	82.99	93.15	89.53	90.38	88.39	82.99
324	54	84.25	93.92	90.54	91.37	89.50	84.25
336	56	85.43	94.60	91.45	92.22	90.39	85.43
348	58	86.56	95.22	92.31	93.02	91.28	86.56

^a Number of patients randomized to dose levels 10 mg, 20 mg, 30 mg, and 40 mg of neladenoson bialanate, for placebo sample size per group to be multiplied by 3/2, for dose level 5 mg sample size per group to be divided by 2.

To achieve at least 80% power for the multiple contrast test in the MCP-Mod approach under all different alternatives, a minimum of 48 patients per treatment group (72 patients for the placebo and 24 patients for the 5 mg group) is needed, resulting in an overall sample size of N = 288 patients.

In the second step, the power for the multiple contrast test in the MCP-Mod approach for the absolute change in log-transformed NT-proBNP was estimated, based on the assumptions outlined in Section 10.3.2.2 and a given sample size of $N = 288$. Statistical simulations were used to assess the power of the Hochberg test to reject at least one of the two null hypotheses. It was concluded that an overall sample size of $N = 288$ patients is sufficient to reject at least one of the two primary efficacy hypotheses with a power of about 83%.

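### The multiple-imputation FAS analysis gives patients who stop study drug roughly an on-drug Week 20 value, although the FAS is meant to describe all randomized patients

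*SAP*

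**What the plan says.** Protocol 10.3.3 gives the two analysis sets different targets. The per-protocol set (PPS) addresses patients who stayed in the study and on treatment to Week 20. For the other set: "The efficacy analysis in the FAS aims at evaluating the dose-response relationship of the primary and secondary efficacy variables for all randomized patients".

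Protocol 6.4.1 says: "All patients who permanently discontinue study medication should come in for the EOT / premature discontinuation visit as soon as possible". In Table 9-1, echocardiography appears only at baseline and at the end-of-treatment (EOT) or premature discontinuation visit. The safety visit four weeks after the last dose includes NT-proBNP but no echo, and the later contact is a phone call. A patient who stops early therefore has no scheduled Week 20 LVEF. The protocol itself does not count the early EOT value as a Week 20 value, since it describes carrying such values forward as imputation.

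SAP 6.2.1.4.2 lists three FAS analyses:

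- the primary method without imputation;
- multiple imputation, with the rule "Generally, it will be assumed that missing observations for the respective efficacy variables are missing at random", an exception and penalties for CV death and HF hospitalization, and an open-ended list of predictors that names the baseline value, treatment group and sex;
- last observation carried forward (LOCF), including the baseline value.

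Protocol 10.3.3 and SAP 4.3 both concede that missing at random (MAR) may not hold, and both promise sensitivity analyses under different assumptions.

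**The concern.** Under MAR with treatment group in the model and no term for being off drug, a patient who stops for intolerance is imputed mainly from same-arm patients who have Week 20 data, most of them still on drug. The result answers the question of what would have happened had these patients continued. That is close to the per-protocol question and is not the stated FAS target.

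This matters because the trial exists to choose a Phase III dose, its primary analysis is per-protocol, and about a quarter of randomized patients are expected not to contribute complete data (Protocol 10.4). Protocol 3.4 names bradycardia and higher-degree AV block as concerns arising from the mechanism. If stopping rises with dose and the effect fades off drug, the benefit across all randomized patients is smaller at the higher doses than this analysis would indicate.

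**Working it through.** **1. The plan's own figures.** Inputs for LVEF are a mean change of +2 on placebo and at most +5 on drug, SD 7 (Protocol 10.3.2.2), one-sided alpha 5% (10.3.2), and allocation as in 10.4: "The overall randomization ratio was assumed to be 3:1:2:2:2:2 for doses 0, 5, 10, 20, 30, and 40 mg". With optimal contrasts, N = 288 and a multivariate t distribution with 288 − 6 = 282 degrees of freedom, the critical value is 1.964.

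| Shape | Stated power (%) | Recomputed (%) |
|---|---|---|
| Linear | 80.31 | 80.3 |
| Sigmoidal Emax 1 | 91.39 | 91.4 |
| Sigmoidal Emax 2 | 87.30 | 87.3 |
| Emax | 88.25 | 88.2 |
| Quadratic | 86.09 | 86.2 |

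Also 288 / 0.75 = 384. The sample-size figures reproduce and are not in question.

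**2. What own-arm MAR imputation returns.** A simulation used 3,000 trials of 384 patients with 10 imputations each, the Emax shape, and baseline, arm and sex in the model. Stopping was assumed at 15/15/15/20/35/50% for placebo and 5/10/20/30/40 mg (25% overall), with stoppers returning to the placebo mean. LVEF differences from placebo:

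| | 5 mg | 10 mg | 20 mg | 30 mg | 40 mg |
|---|---|---|---|---|---|
| Own-arm MAR imputation | 2.46 | 2.75 | 2.93 | 2.98 | 3.02 |
| Completers only | 2.45 | 2.74 | 2.92 | 2.98 | 3.02 |
| All randomized, effect lost on stopping | 2.09 | 2.34 | 2.35 | 1.94 | 1.49 |
| Baseline carried forward | 2.09 | 2.33 | 2.24 | 1.54 | 0.81 |

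The imputation reproduces the completers' result. Carrying baseline forward does show the loss.

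**3. Stopping at one rate in every arm.** If stoppers return to the placebo mean, the all-randomized effect is effect × (1 − p), where p is the share who stop in the active arm. With p = 10%: 3.0 × 0.90 = 2.70. With p = 25%: 3.0 × 0.75 = 2.25. At 25%, power with all 384 patients would be 69.5% (Linear) to 83.0% (Sigmoidal Emax 1), against 80.3% to 91.4% for 288 completers. These powers keep SD 7 and ignore imputation and mixture variance, so they are slightly optimistic.

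**4. Stopping that rises with dose.** Assume 12/18/26/35% at 10/20/30/40 mg. Each cell is the Protocol Table 10-1 difference from placebo, then that difference × (1 − p). For example, Emax at 40 mg is 3.09375 × 40 / 41.25 = 3.00, and 3.00 × 0.65 = 1.95.

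| Shape | 10 mg | 20 mg | 30 mg | 40 mg | Peak after stopping |
|---|---|---|---|---|---|
| Emax | 2.75 → 2.42 | 2.91 → 2.39 | 2.97 → 2.20 | 3.00 → 1.95 | 10 mg |
| Sigmoidal Emax 1 | 1.82 → 1.60 | 2.89 → 2.37 | 2.98 → 2.21 | 3.00 → 1.95 | 20 mg |
| Sigmoidal Emax 2 | 0.38 → 0.33 | 1.69 → 1.38 | 2.60 → 1.93 | 3.00 → 1.95 | 40 mg |
| Linear | 0.75 → 0.66 | 1.50 → 1.23 | 2.25 → 1.67 | 3.00 → 1.95 | 40 mg |
| Quadratic | 1.67 → 1.47 | 2.67 → 2.19 | 3.00 → 2.22 | 2.67 → 1.74 | 30 mg |

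The top of the curve turns down for Emax and Sigmoidal Emax 1. Linear and Sigmoidal Emax 2 still rise. The Quadratic peak stays at 30 mg, where it was before any stopping.

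**The case against.** The strongest reply is that this is one of three FAS sensitivity analyses, and the others matter. LOCF gives a change of 0 to a patient with only a baseline echo. That is below the assumed placebo mean of +2, so it is harsher than a placebo-based imputation. This stands, but as partial cover. A patient who attends the early EOT echo has a value from soon after the last dose carried forward, which can keep on-drug benefit. The protocol itself calls LOCF usually biased.

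A reader might infer three stronger things that the documents do not support:

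- *That the FAS merely repeats the PPS.* The FAS analyses patients as randomized and keeps non-adherent patients and eligibility violators who have Week 20 values. The PPS removes them and analyses as treated. The simulation above isolates stopping and does not show overall agreement between the two sets.
- *That the plan conceals the problem.* Discontinuations and their reasons are reported by arm, adverse events leading to withdrawal or interruption are tabulated, unbalanced withdrawal is to be explored further, and dose choice weighs safety. No method is named for that exploration, however.
- *That the imputed analysis would display a misleading rising curve, or that dose ordering reverses in general.* Protocol 10.3.3 applies only the testing step to the imputed data, and SAP Appendix 9.4 pools a contrast and its variance, so no fitted curve is specified. Reversal depends on the shape, as step 4 shows.

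Two ambiguities remain. Step 2 of the imputation does not say whose values are penalized. The wording before it points to CV death and HF hospitalization only. If every imputed value were penalized, this concern would fail for that analysis, and tolerability stoppers would instead receive a worst-change penalty. The predictor list is also open-ended, so off-drug information could be added, but nothing commits to it.

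**Conclusion.** The concern holds for patients who stop study drug for reasons other than CV death or HF hospitalization. For them, the multiple-imputation FAS analysis estimates roughly the effect under continued treatment, which differs from the stated target, and neither of the other two FAS analyses fully corrects this. It also does not supply the different assumption about missingness that the plan promises for these patients.

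The size rests on assumptions the documents do not quantify. If the effect is lost by Week 20 after stopping, 10 to 25% stopping overstates a true 2.7 to 2.25 points as about 3.0. The documents give only about 25% without complete data overall. That figure includes invalid data and is not split by dose, so 25% stopping is an illustration. A downturn at the top doses needs dose-related stopping as well, and occurs under two of the five candidate shapes at the rates assumed here. This is a worthwhile, inexpensive improvement to a sensitivity analysis; the primary analysis and the power figures are unaffected.

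**What to change.** In SAP 6.2.1.4.2:

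- Add a reference-based multiple imputation. For patients who permanently stopped study drug for reasons other than CV death or HF hospitalization, draw Week 20 values from a model based on the placebo arm. Keep the current MAR version alongside it.
- State whether an early EOT echo enters that model, since conditioning on it can bring on-drug benefit back in.
- For NT-proBNP, use the sample taken four weeks after the last dose where it exists, as off-drug information.
- State that the step 2 penalty applies only to values missing because of CV death or HF hospitalization.
- Report the pooled contrast test and the arm means under both assumptions.

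The cost is one SAP paragraph and one additional imputation run on data already scheduled. The downside is a somewhat less favourable FAS estimate.
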